4.1 Description of study design

This is a Phase III, global, multi-center, randomized, double-blind, placebo-controlled study. The study design is placebo-controlled during the first 12 weeks, followed by open-label treatment with osilodrostat until week 48, and an optional Extension phase.

Screening period (up to 8 weeks):

[figure not shown]
The screening period will have a maximum duration of 8 weeks to enable patients to washout their current treatment for Cushing’s disease. Patients will be evaluated for trial eligibility after the washout period is completed.

During washout, some patients may have loss of control of co-morbidities such as hypertension and diabetes. Therefore the screening period should be viewed as a “run-in” period in which the treatment of co-morbidities is optimized. Patients should be closely monitored and treated accordingly, aiming ideally for normalization of blood pressure, fasting glucose and potassium. Control of co-morbidities in this “run-in” is important for patient safety and to ensure the majority of patients can complete the 12-week placebo-control period and therefore minimize loss of data. Three 24-hr UFC urine samples and two late night salivary cortisol samples are to be collected after completion of the washout period to assess study eligibility.

Period 1 (Weeks 1-12): double-blind, placebo-controlled period

This is the randomized, double-blind, placebo-controlled period (Weeks 1-12). Eligible patients are randomized in a 2:1 ratio to treatment with study drug (osilodrostat or placebo, respectively). Patients are stratified at randomization according to history of pituitary irradiation (yes/no).

Figure 4-1 Schematic of Period 1

[figure not shown]
*Patients are randomized in a 2:1 ratio to osilodrostat (LCI699) or placebo

** LCI699 Dose determined by Independent Endocrinologists. Intermediate doses may be used in specific circumstances. Please see Section 6.2 for details.

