5.2 Inclusion criteria

Patients eligible for inclusion in this study have to meet **all** of the following criteria:

1. Written informed consent obtained before any assessment is performed.
2. Male or female patients aged 18 - 75 years.
3. Confirmed CD that is persistent or recurrent as evidenced by all of the following criteria being met (i.e., a, b, and c):
 - a. $mUFC > 1.3 \times ULN$ (Mean of three 24-hour urine samples collected preferably on 3 consecutive days during screening after washout of prior medical therapy for CD (if applicable), confirmed by the central laboratory and available before Day 1), with ≥ 2 of the individual UFC values being $> 1.3 \times ULN$.
 - b. Morning plasma ACTH above Lower Limit of Normal
 - c. Confirmation (based on medical history) of pituitary source of excess ACTH as defined by any one or more of the following three criteria:
 - i. Histopathologic confirmation of an ACTH-staining adenoma in patients who have had prior pituitary surgery.
OR
 - ii. MRI confirmation of pituitary adenoma > 6 mm
OR
 - iii. Bilateral inferior petrosal sinus sampling (BIPSS) with either CRH or DDAVP stimulation for patients with a tumor ≤ 6 mm. The criteria for a confirmatory BIPSS test are any of the following:
 - Pre-dose central to peripheral ACTH gradient > 2 ;

- Post-dose central to peripheral ACTH gradient > 3 after either CRH or DDAVP stimulation
4. Patients that received glucocorticoid replacement therapy must have discontinued such therapy for at least seven days or 5 half-lives prior to screening, whichever is longer.
 5. Patients with *de novo* CD can be included only if they are not considered candidates for surgery (e.g., poor surgical candidates due to co-morbidities, inoperable tumors, patients who refuse to have surgical treatment, or surgical treatment is not available)
 6. For patients with a history of pituitary irradiation: at least 2 years for stereotactic radiosurgery (SRS), and 3 years for conventional (fractionated) radiation, respectively, must have elapsed from the time of the most recent radiation treatment to the time of enrollment into this study.
 7. Able to communicate well with the investigator, to understand and comply with the requirements of the study.
 8. Washout of any current drug therapy for CD. The following minimum washout periods must be completed before baseline efficacy assessments are performed:
 - a. Steroidogenesis inhibitors (ketoconazole, metyrapone): 1 week

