7.1 Study flow and visit schedule

Table 7-1a, Table 7-1b and Table 7-2 list all of the assessments and indicate the visits at which they are performed with an “X” for the Core and Extension phases, respectively. Visit assessments window is ± 3 days, except for Day 1 which has a +3 day window.

All data obtained from these assessments must be supported in the patient’s source documentation. The table indicates which assessments produce data to be entered into the clinical database (D) or remain in source documents only (S) (“Category” column).

No eCRF will be used as a source document.

Table 7-3, Table 7-4, Table 7-5, Table 7-6, Table 7-7, [REDACTED] and Table 7-11 list all of the assessments required for the collection plan for Disease and Imaging Assessment, Clinical Laboratory parameters, Imaging, ECG, PK samples, Biomarkers samples, PPD [REDACTED] and Patient Reported Outcome, respectively.

Patients must end participation in the optional extension period within 4 weeks after Protocol Amendment 02 is approved at the site, or by Week 96, whichever occurs first.

Table 7-1a Visit evaluation schedule – Core – Period 1

	Category	Protocol Section	Screening			Core Treatment					Post-Treatment Follow-up				
			Wash-out	Post wash-out		Period 1					For patients discontinuing during Period 1				
Day			from -56	up to -15	-14 to -1	1	15	36	57	85	15	36	57	85	Last dose +30d
Week			from -8	up to -3	-2 to -1	1	2	5	8	12	2	5	8	12	
Obtain Informed consent	D	7.1.1	x												
IRT Contact	S		x			x	x	x	x	x				x	
IRT Randomization	S					x									
Patient history															
Demography	D	7.1.1.3	x												
Inclusion/Exclusion criteria	D	5.2 & 5.3			x										
Relevant medical history/Current medical conditions	D	7.1.1.3	x												
Cushing's Disease history	D	7.1.1.3	x												
Prior/concomitant medication	D	7.1.1.3				As required									
Physical examination	S	7.2.2.1	x			x	x	x	x	x	x	x	x	x	x
Body height	D	7.2.2.3	x												
Body weight and Waist Circumference	D	7.2.2.3	x			x	x	x	x	x	x	x	x	x	x
Physical features of Cushing's disease	D	7.2.1.2	x							x				x	
Signs and symptoms of adrenal insufficiency	D	7.2.2.1.1				x	x	x	x	x	x	x	x	x	x
Vital signs															
Body temperature/ Blood pressure/Pulse rate	D	7.2.2.2	x			x	x	x	x	x	x	x	x	x	x
Laboratory assessments															

	Category	Protocol Section	Screening			Core Treatment					Post-Treatment Follow-up				
			Wash-out	Post wash-out		Period 1					For patients discontinuing during Period 1				

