7.1.1.3 Patient demographics and other baseline characteristics

The following patient demographics and baseline characteristics will be collected on the eCRF:

- Demography including date of birth, sex, predominant race and ethnicity (where permitted).
- Height, weight and waist circumference (see [Section 7.2.2.3](#)).
- Medical history (e.g., important medical, surgical, and allergic conditions from the patient's medical history which could have an impact on the patient's evaluation) / current medical conditions (e.g., all relevant current medical conditions which are present at the time of signing informed consent). Ongoing medical conditions, symptoms and diseases which are recorded on the Medical History eCRF should include the toxicity grade when applicable.
- Information on the most recent prior medical therapy for CD will be collected and will include information on drug, dose, duration of therapy and outcomes provided such data are available.
- Where possible, diagnoses and not symptoms will be recorded. Cushing's disease history together with the medication/treatment used will be collected.
- Prior and concomitant medications.

All assessments to be completed and documented during screening and at baseline are detailed in [Table 7-1a](#).

Day 1 assessments / samples should be taken before the patient receives study drug as these values will be considered the baseline values for the study. Where multiple values are available for a parameter prior to study drug, the last value prior to the start of study drug will be considered the baseline value.

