7.2 Assessment types

7.2.1 Efficacy assessments

Table 7-3 Disease and Imaging Assessment collection plan

Procedure	Screening	During Treatment/Follow-up
24-hour urine samples to test for Urine Free Cortisol and creatinine	Mandated at screening (post washout)	Mandated for Periods 1 and 2, the optional Extension and the 30 day Post Treatment Follow-up, as detailed in Table 7-1a , Table 7-1b and Table 7-2 . *Every effort should be made to collect samples for patients discontinuing treatment prior to Week 12 during Period 1 per Table 7-1a . Three 24-hour samples are to be collected at screening, Day 1, Week 12, Week 36, Week 48 and Week 12 Post-Treatment follow-up visit. Two 24-hour samples are to be collected at all other study time points.
Physical features of CD	Mandated at screening	Mandated for Periods 1 and 2, the optional Extension and the 30 day Post Treatment follow-up, as detailed in Table 7-1a , Table 7-1b and Table 7-2 .
DXA scan (lumbar spine and total hip)	Mandated at screening	Mandated at End of Treatment Core and End of Treatment Extension, unless EOT occurs less than 6 months before the scheduled Week 96 visit.

* For patients who discontinued study drug during Period 1.

All urine samples will be sent to the central laboratory designated by Novartis for assessment. During Period 1, once results are available, an alert (by email or fax) will be sent to the IE. The central laboratory and the IE will ensure that the sites and Novartis remain blinded to the results.

Starting from Week 14 in Period 2, UFC results will be sent directly by the central laboratory to the investigators.

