7.2.1.2 Physical features of Cushing's disease

The following clinical signs (physical findings) of Cushing's disease will be assessed clinically for severity at time points defined in Table 7-1a, Table 7-1b, Table 7-2 and Table 7-3: facial rubor, hirsutism (female only), striae, supraclavicular and dorsal fat pads, proximal muscle wasting (atrophy), central (abdominal) obesity, and ecchymoses (bruising). These clinical signs are to be rated on a semi-quantitative scale as follows: 0=absent; 1=mild; 2=moderate; and 3=severe.

Physical features of Cushing's disease will also be documented by photography. A total of four photographs will be taken. Two photographs, one frontal and one lateral from the shoulders up will be taken to assess facial plethora (rubor), supraclavicular and dorsal fat pads. Two photographs, frontal and dorsal of the trunk with patient in standing position will be taken to assess striae, proximal muscle wasting (atrophy), central (abdominal) obesity, and ecchymoses (bruising). In order to maintain confidentiality, photographs will not be published without the explicit written consent of the patient. Photographs will be centrally collected and checked for quality by an imaging vendor. The quality checks will be detailed in the vendor manual.

If for cultural reasons, usual lifestyle, or other reasons, photographic assessments cannot be performed, this must be discussed with the sponsor on a case-by-case basis and sponsor approval will be required.

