2.7.6 Assess the change from baseline in physical features of Cushing's disease

For each of physical features of Cushing's disease: facial rubor, striae, supraclavicular fat pad, dorsal fat pad, proximal muscle wasting (atrophy), central (abdominal) obesity, and ecchymoses (bruises), Likert scores will be measured. The change from baseline at Weeks 12, 36 and 48 will be assessed by shift tables in each of the randomized treatment arms. The change will also be provided for overall patients in open-label period. In addition, the proportions of patients having a favourable shift from baseline to post-baseline time points will be tabulated. FAS will be used for this analysis.

2.7.7 Assess the change from baseline in bone mineral density by DXA scan at Week 48

For bone mineral density measured by DXA scan at the lumbar spine and total hip, descriptive summaries of actual and percentage change from baseline to Week 48 will be provided by randomized treatment arm and for overall patients. FAS will be used for this analysis.

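### The schedule does not ensure an off-drug baseline for the physical-features rating, and it is not reconciled with inclusion criterion 8

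*Protocol*

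**What the plan says.** Change in physical features at Weeks 12, 36 and 48 is a secondary objective (Protocol, Table 3-1). Section 7.2.1.2 rates each sign from 0 (absent) to 3 (severe), adds photographs, and leaves timing to the schedule: the signs "will be assessed clinically for severity at time points defined in" the visit tables and Table 7-3.

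In Table 7-1a the row "Physical features of Cushing's disease" is marked once before treatment, in the Wash-out column. Section 4.1 describes that period: "The screening period will have a maximum duration of 8 weeks to enable patients to washout their current treatment". The next mark is Week 12. Table 7-3 ties the screening urine collection to the time after washout but, for physical features, specifies only screening.

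Three other provisions bear on this:

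- Inclusion criterion 8 (Section 5.2): "The following minimum washout periods must be completed before baseline efficacy assessments are performed".
- The baseline rule (Section 7.1.1.3): "Day 1 assessments / samples should be taken before the patient receives study drug as these values will be considered the baseline values for the study". With several pre-dose values, "the last value prior to the start of study drug will be considered the baseline value". Section 2.1.1 of both SAPs likewise takes the last assessment on or before the start of treatment.
- The analysis (core SAP, Section 2.7.6): "The change from baseline at Weeks 12, 36 and 48 will be assessed by shift tables in each of the randomized treatment arms". The same section tabulates the proportion of patients with a favourable shift. The final SAP keeps that summary at scheduled visits.

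**The concern.** A site that follows Table 7-1a can rate and photograph a patient when washout begins, while the effect of the earlier drug persists. No later pre-dose rating is scheduled, so that one becomes the baseline. A site that follows criterion 8 waits until washout is complete. Baselines may then mean different things in different patients, and neither SAP distinguishes them.

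The interest lies in what happens on osilodrostat. If a sign worsens when the earlier drug is withdrawn, a rating made before that worsening understates later improvement. A sign rated 0 under earlier therapy cannot shift favourably at all. Weeks 36 and 48 are most exposed because there is no concurrent control by then, so relapse during washout cannot be separated from drug effect.

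**Working it through.** The plan states no figure on this point to reproduce. The check is a reading of the schedule followed by day arithmetic.

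**1. The schedule row.** Table 7-1a has 13 visit columns. The physical-features row is marked in column 1 (Wash-out), column 8 (Day 85) and column 12 (Day 85 follow-up after early discontinuation). Columns 2 to 4 (the two post wash-out columns and Day 1) are blank. The body weight, urinary free cortisol, DXA and CushingQoL rows also have 13 cells and line up, so the reading does not come from a shifted column.

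**2. Comparison with other rows.**

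| Assessment | Wash-out | Post wash-out | Day 1 |
|---|---|---|---|
| Physical features | yes | no | no |
| Weight and waist; vital signs | yes | no | yes |
| Urinary free cortisol | no | yes | yes |
| DXA | no | yes | no |
| CushingQoL | no | no | yes |

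Every other assessment listed has a mark after washout or on Day 1. Physical features has neither.

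**3. Does criterion 8 apply?** Yes. The protocol summary lists physical features under efficacy assessments, and Section 7.2.1.2 falls within the efficacy section. Criterion 8 therefore calls for a rating after washout, while Table 7-1a puts it in the Wash-out column. The passages are not reconciled.

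**4. How early can the rating be?** SAP Section 2.1.1 has no Day 0, so Day -56 precedes Day 1 by 56 days. The span of the change is (visit day - 1) from Day 1, and 56 days more from Day -56:

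| Visit | From Day 1 | From Day -56 |
|---|---|---|
| Week 12 (Day 85) | 84 days | 84 + 56 = 140 days (20 weeks) |
| Week 36 (Day 253) | 252 days | 252 + 56 = 308 days |
| Week 48 (Day 337) | 336 days | 336 + 56 = 392 days |

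These are upper limits, because the Wash-out column gives a start day only.

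**5. Can the rating precede completed washout?** Suppose the earlier drug is last taken on Day -56. With the minimum periods in criterion 8, washout is complete:

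- 7 days later, Day -49, for steroidogenesis inhibitors and subcutaneous pasireotide;
- 21 days later, Day -35, for mifepristone;
- 28 days later, Day -28, for dopamine or PPAR-gamma agonists;
- 56 days later, Day 1, for pasireotide LAR.

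A rating at the opening of the column precedes all of these.

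**6. Size.** For one patient, recorded change = change between rating and Day 1 + change from Day 1 to the visit. If a share p of patients is rated before washout is complete, and d is their mean change from rating to Day 1, the overall mean is offset by p × d. The documents give neither p nor d. If nobody entered on a Cushing's drug, p = 0 and the offset is zero.

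**Limit of the check.** The Period 2 row for this assessment is not visible in the text available. Weeks 36 and 48 are taken from the objectives and the SAP.

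**The case against.** The strongest reply is that the protocol, read as a whole, does not direct an on-drug rating. Criterion 8 forbids a baseline efficacy assessment before washout is complete. Screening in Table 7-3 includes its post wash-out part, and the Wash-out column has no end day. This stands against any claim that the baseline is always on-drug, but it does not settle which passage a site would follow.

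Second, the longest washouts (pasireotide LAR, mitotane) may use rescreening. Section 7.1.1 then requires everything except MRI or CT and DXA to be repeated (those too if more than 60 days have passed). Rescreened patients are therefore re-rated, and the later value counts. That narrows the group at risk. It does not cover patients who wash out within one screening period.

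Third, the signs may not move much over a short washout. Section 1.1.1 notes that recovery from co-morbidities can be slow or incomplete. On the other side, Section 7.2.6 shortens the CushingQoL recall period because symptoms are expected to change quickly once treatment stops, and Section 4.1 anticipates some loss of co-morbidity control during washout. None of this gives a rate for striae, fat pads or muscle wasting, so the size remains open.

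Fourth, the endpoint is one of many other secondary endpoints and is summarised descriptively, without a test. That limits the consequence and is accepted.

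**Conclusion.** The point holds as an unreconciled inconsistency: Tables 7-1a and 7-3 do not ensure a post-washout baseline for physical features, and criterion 8 requires one. Only patients with a Cushing's drug to wash out, and not re-rated on rescreening, are exposed. For them the within-arm and pooled results at Weeks 36 and 48 can combine withdrawal of earlier therapy with the effect of osilodrostat. If signs worsen in washout, the distortion runs against osilodrostat.

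Three stronger readings are tempting and are not supported:

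- A reader might infer that change is never measured from an untreated baseline. Criterion 8 and the rescreening rule contradict this, and patients with no current Cushing's drug are unaffected.
- A reader might infer that the Week 12 comparison is biased. Both arms share the schedule and the rating precedes randomised treatment, so there is no bias by arm in expectation, only added variability.
- A reader might attach a number of scale points to the bias. That needs an assumed share and an assumed worsening. The documents supply neither, and zero is possible for both.

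**What to change.** **Schedule.** Reconcile Tables 7-1a and 7-3 with criterion 8 by moving the rating and photographs from the Wash-out column to Day 1 pre-dose, or to Day -14 to -1. The assessment is moved, not added, and Table 7-1a already has a physical examination on Day 1.

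**Analysis.** The Amendment 2 rationale states that the study is fully enrolled, so the schedule change cannot repair existing baselines. For these patients, add to SAP Section 2.7.6:

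1. the number of baseline ratings made before the criterion 8 washout was complete, by arm and overall;
2. the same shift tables and favourable-shift proportions, restricted to patients who on the rating date were not on a Cushing's drug or had completed its washout.

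The final SAP records that the core results have been reported, so the restricted table should be labelled as added afterwards. Status on the rating date is fixed before randomisation, so the restriction leaves the Week 12 comparison a randomised one.

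**Cost.** Schedule wording, one count and one extra descriptive table with a smaller n. The restricted patients may differ from the rest in treatment history, so the table is a check on the main result, not a replacement for it. Section 6.4 already requires medication start and stop dates. Details of the most recent Cushing's therapy are collected where available (Section 7.1.1.3), so some patients may be unclassifiable and should be counted as such.

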7.1.1 Screening

Written main informed consent must be obtained before any study specific assessments are performed. IRT will be contacted to register the patient at screening.

The screening assessments must be performed within 56 days before the first study drug dose on Day 1.

When applicable, patients must have undergone washout of any current drug therapy for CD according to washout periods described in the Inclusion criteria ([Section 5.2](#)). During washout, some patients may have loss of control of co-morbidities such as hypertension and diabetes. Therefore the screening period should be viewed as a “run-in” period in which the treatment of co-morbidities is optimized. Patients should be closely monitored and treated accordingly, aiming ideally for normalization of blood pressure, fasting glucose and potassium.

Information on the most recent prior medical therapy for CD will be collected including the drug name, dose, duration of therapy and outcome, provided such data are available.

The three 24-hour urine samples for the mUFC value eligibility assessment should be collected. In addition, two late night salivary cortisol samples need to be collected to exclude pseudo-cushing’s disease ([Alwani et al 2014](#)). These urine and saliva samples should be collected after the washout period is over, in order to avoid any interference with the washed out therapy. It is highly recommended to send them to the central laboratory at least 14 days prior to Day 1 in order to ensure that sufficient time is allowed for central laboratory results to become available prior to Day 1.

For laboratory evaluations used to determine eligibility, repeated evaluation within the screening window is permitted for screening results out of the defined range. If laboratory results are pending at the end of the screening period, the screening period will be extended until the results become available to site. If the latest repeated laboratory result(s) meet the criteria, those results may be used to determine eligibility. If the latest repeated laboratory result(s) do not meet the criteria, the patient will be considered a screening failure.

Patients who do not meet eligibility criteria are allowed to be rescreened up to a maximum of two times. The rescreening should be documented in the source files and re-registered in IRT. If a patient is re-screened the patient should retain their study Subject Number.

If rescreening is within 60 days of the end of the original screening period, the following procedures do not have to be repeated: pituitary MRI (or CT) and DXA scan. All other assessments must be repeated.

If rescreening is done more than 60 days after the end of original screening period, all assessments must be repeated.

For details of assessments and day windows, refer to [Table 7-1a](#).

An additional biomarker informed consent will be proposed to the patient for optional participation. For details, refer to [Section 7.2.4.2](#).

